21. APPENDIX C: MANAGEMENT ALGORITHMS FOR IMMUNE-MEDIATED ADVERSE EVENTS

Recommended Management of Immune-mediated AEs. Will not be considered deviations/violations if not followed exactly.

GI Adverse Event Management Algorithm

[figure not shown]
Rule out non-inflammatory causes. If non-inflammatory cause is identified, treat accordingly and continue I-O therapy. Opiates/narcotics may mask symptoms of perforation. Infliximab should not be used in cases of perforation or sepsis.

Patients on IV steroids may be switched to an equivalent dose of oral corticosteroids (e.g. prednisone) at start of tapering or earlier, once sustained clinical improvement is observed. Lower bioavailability of oral corticosteroids should be taken into account when switching to the equivalent dose of oral corticosteroids.

Renal Adverse Event Management Algorithm

[figure not shown]
Rule out non-inflammatory causes. If non-inflammatory cause, treat accordingly and continue I-O therapy

Patients on IV steroids may be switched to an equivalent dose of oral corticosteroids (e.g. prednisone) at start of tapering or earlier, once sustained clinical improvement is observed. Lower bioavailability of oral corticosteroids should be taken into account when switching to the equivalent dose of oral corticosteroids.

Pulmonary Adverse Event Management Algorithm

[figure not shown]
Rule out non-inflammatory causes. If non-inflammatory cause, treat accordingly and continue I-O therapy. Evaluate with imaging and pulmonary consultation.

Patients on IV steroids may be switched to an equivalent dose of oral corticosteroids (e.g. prednisone) at start of tapering or earlier, once sustained clinical improvement is observed. Lower bioavailability of oral corticosteroids should be taken into account when switching to the equivalent dose of oral corticosteroids.

Hepatic Adverse Event Management Algorithm

Rule out non-inflammatory causes. If non-inflammatory cause, treat accordingly and continue I-O therapy. Consider imaging for obstruction.

[figure not shown]
Patients on IV steroids may be switched to an equivalent dose of oral corticosteroids (e.g. prednisone) at start of tapering or earlier, once sustained clinical improvement is observed. Lower bioavailability of oral corticosteroids should be taken into account when switching to the equivalent dose of oral corticosteroids.

*I-O therapy may be delayed rather than discontinued if AST/ALT ≤ 8 x ULN and T.bili ≤ 5 x ULN.

**The recommended starting dose for grade 4 hepatitis is 2 mg/kg/day methylprednisolone IV.

Endocrinopathy Management Algorithm

[figure not shown]
Rule out non-inflammatory causes. If non-inflammatory cause, treat accordingly and continue I-O therapy. Consider visual field testing, endocrinology consultation, and imaging.

Patients on IV steroids may be switched to an equivalent dose of oral corticosteroids (e.g. prednisone) at start of tapering or earlier, once sustained clinical improvement is observed. Lower bioavailability of oral corticosteroids should be taken into account when switching to the equivalent dose of oral corticosteroids.

Skin Adverse Event Management Algorithm

Rule out non-inflammatory causes. If non-inflammatory cause, treat accordingly and continue I-O therapy.

[figure not shown]

Patients on IV steroids may be switched to an equivalent dose of oral corticosteroids (e.g. prednisone) at start of tapering or earlier, once sustained clinical improvement is observed. Lower bioavailability of oral corticosteroids should be taken into account when switching to the equivalent dose of oral corticosteroids.

*Refer to NCI CTCAE v4 for term-specific grading criteria.

Neurological Adverse Event Management Algorithm

Rule out non-inflammatory causes. If non-inflammatory cause, treat accordingly and continue I-O therapy.

Patients on IV steroids may be switched to an equivalent dose of oral corticosteroids (e.g. prednisone) at start of tapering or earlier, once sustained clinical improvement is observed. Lower bioavailability of oral corticosteroids should be taken into account when switching to the equivalent dose of oral corticosteroids.

22. APPENDIX D: DANA-FARBER/HARVARD CANCER CENTER MULTI-CENTER DATA AND SAFETY MONITORING PLAN TABLE OF CONTENTS

1. INTRODUCTION.....	83
1.1 Purpose	83
1.2 Multi-Center Data and Safety Monitoring Plan Definitions	83
2. GENERAL ROLES AND RESPONSIBILITIES	84
2.1 DF/HCC Sponsor	84
2.2 Coordinating Center	85
2.3 Participating Institution	85
3. DF/HCC REQUIREMENTS FOR MULTI-CENTER PROTOCOLS	86
3.1 Protocol Distribution	86
3.2 Protocol Revisions and Closures	86
3.3 Informed Consent Requirements	86
3.4 IRB Documentation	87
3.5 IRB Re-Approval	87
3.6 Participant Confidentiality and Authorization Statement	87
3.7 DF/HCC Multi-Center Protocol Registration Policy	88
3.8 DF/HCC Protocol Case Number	89
3.9 Safety Assessments and Toxicity Monitoring	90
3.10 Data Management	91

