7.2 Criteria to Resume Treatment with Nivolumab with or without Ipilimumab

Nivolumab and/or ipilimumab should be administered as soon as the subject meets criteria to resume treatment. If a dose has been missed for combination therapy, the subject should not wait until the next scheduled dosing date but can restart when clinically safe as long as it has been at least 3 weeks from last ipilimumab. If a dose is held or missed for single agent nivolumab, the subject should resume treatment at the next scheduled dosing date. Efforts should be made to administer as many doses as possible, if a subject cannot be treated on a particular day the cycle should either be skipped or frame shifted to a point when the patient is able to be treated. All efforts should be made to refrain from skipping doses of Ipilimumab. If a subject has been holding for an extended period of time or clarifying questions are needed in regards to resuming treatment please reach out to the Principal Investigator

Subjects may resume treatment with study drug when the drug-related AE(s) resolve to Grade \leq 1 or baseline value, with the following EXCEPTIONS:

- Subjects may resume treatment in the presence of Grade 2 fatigue.
- Subjects who have not experienced a Grade 3 drug-related skin AE may resume treatment in the presence of Grade 2 skin toxicity.
- Subjects with baseline Grade 1 AST/ALT or total bilirubin who require dose delays for reasons other than a 2-grade shift in AST/ALT or total bilirubin may resume treatment in the presence of Grade 2 AST/ALT OR total bilirubin.
- Subjects with combined Grade 2 AST/ALT AND total bilirubin values meeting discontinuation parameters (Section 7.3) should have treatment permanently discontinued.
- Drug-related pulmonary toxicity, diarrhea, or colitis, must have resolved to baseline before treatment is resumed.
- Drug-related endocrinopathies adequately controlled with only physiologic hormone replacement may resume treatment.

If treatment is delayed $>$ 6 weeks, the subject must be permanently discontinued from study therapy, except as specified in Section 7.3. If irAEs require management with systemic steroids, dosing may resume once patient is tolerating prednisone 10 mg/day equivalent or lower.

For the period in which ipilimumab is administered with nivolumab, treatment must be resumed on the same day. If a subject is unable to resume both nivolumab and ipilimumab within 6 weeks of dose interruption, permanent discontinuation is required.

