
7.3 Criteria to Discontinue Treatment with Nivolumab with or without Ipilimumab

Treatment with nivolumab with or without ipilimumab should be permanently discontinued for any of the following:

- Any Grade 2 drug-related uveitis or eye pain or blurred vision that does not respond to topical therapy and does not improve to Grade 1 severity within the re-treatment period OR requires systemic treatment
- Any Grade 3 non-skin, drug-related adverse event lasting $>$ 7 days, with the following exceptions for drug-related laboratory abnormalities, uveitis, pneumonitis, bronchospasm, diarrhea, colitis, neurologic toxicity, hypersensitivity reactions, and infusion reactions:

- Grade 3 drug-related uveitis, pneumonitis, bronchospasm, diarrhea, colitis, neurologic toxicity, hypersensitivity reaction, or infusion reaction of any duration requires discontinuation
- Grade 3 drug-related laboratory abnormalities do not require treatment discontinuation except:
 - Grade 3 drug-related thrombocytopenia > 7 days or associated with bleeding requires discontinuation
 - Any drug-related liver function test (LFT) abnormality that meets the following criteria require discontinuation:
 - * AST or ALT > 8 x ULN
 - * Total bilirubin > 5 x ULN
 - * Concurrent AST or ALT > 3 x ULN and total bilirubin > 2 x ULN
- Any Grade 4 drug-related adverse event or laboratory abnormality, except for the following events which do not require discontinuation:
 - Grade 4 amylase or lipase abnormalities that are not associated with symptoms or clinical manifestations of pancreatitis. It is recommended to consult with the PI for Grade 4 amylase or lipase abnormalities.
 - Isolated Grade 4 electrolyte imbalances/abnormalities that are not associated with clinical sequelae and are corrected with supplementation/appropriate management within 72 hours of their onset
- Any dosing interruption lasting > 6 weeks unless the sponsor-investigator is consulted and agrees with the rationale for resuming therapy after a delay > 6 weeks. Note that tumor assessments should continue as per protocol even if dosing is interrupted.
- Any adverse event, laboratory abnormality, or intercurrent illness which, in the judgment of the site investigator, presents a substantial clinical risk to the subject with continued nivolumab with or without ipilimumab dosing.

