12.6 Routine Adverse Event Reporting

All Adverse Events **must** be reported in routine study data submissions to the Overall PI on the toxicity case report forms. **AEs reported through expedited processes (e.g., reported to the IRB, FDA, etc.) must also be reported in routine study data submissions.**

Abnormal laboratory values or diagnostic test results constitute AEs only if they induce clinical signs or symptoms or require treatment or further diagnostic tests.

Wherever possible, timely confirmation of initial liver-related laboratory abnormalities should occur prior to the reporting of a potential drug-induced liver injury (DILI) event. All occurrences of potential DILIs, meeting the defined criteria, must be reported as SAEs.

Potential drug induced liver injury is defined as:

- 1) AT (ALT or AST) elevation > 3 times upper limit of normal (ULN)

AND

- 2) Total bilirubin > 2 times ULN, without initial findings of cholestasis (elevated serum alkaline phosphatase)

AND

- 3) No other immediately apparent possible causes of AT elevation and hyperbilirubinemia, including, but not limited to, viral hepatitis, pre-existing chronic or acute liver disease, or the administration of other drug(s) known to be hepatotoxic.

Hospitalization for elective surgery or routine clinical procedures that are not the result of an AE (e.g., surgical insertion of central line) should not be recorded as an AE.

Disease progression should not be recorded as an AE, unless it is attributable to the study regimen by the site investigator.

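### The Appendix C hepatic footnote, as worded, allows a delay for combined AST/ALT and bilirubin elevations that Section 7.3 says require permanent discontinuation

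*Combined protocol and SAP*

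**What the plan says.** Section 7.3 opens with "Treatment with nivolumab with or without ipilimumab should be permanently discontinued for any of the following". For the liver it adds "Any drug-related liver function test (LFT) abnormality that meets the following criteria require discontinuation" and lists three criteria: AST or ALT above 8 x ULN, total bilirubin above 5 x ULN, and "Concurrent AST or ALT > 3 x ULN and total bilirubin > 2 x ULN".

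Section 7.2, on resuming treatment, points back to that list: "Subjects with combined Grade 2 AST/ALT AND total bilirubin values meeting discontinuation parameters (Section 7.3) should have treatment permanently discontinued".

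Section 7.4 refers site investigators to Appendix C for guidance on immune-mediated adverse events. The Appendix C header calls its content recommended management and says that not following it exactly is not a deviation or violation. The footnote to its hepatic algorithm reads "I-O therapy may be delayed rather than discontinued if AST/ALT ≤ 8 x ULN and T.bili ≤ 5 x ULN".

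Section 12.6 uses the same two thresholds, above 3 x ULN for ALT or AST and above 2 x ULN for total bilirubin, in its definition of potential drug-induced liver injury (DILI). That definition also requires no initial cholestasis and no other immediately apparent cause. For such cases, "All occurrences of potential DILIs, meeting the defined criteria, must be reported as SAEs".

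**The concern.** The 8 x and 5 x ULN limits in the footnote are the limits of the first two Section 7.3 criteria, turned round to say when a delay is enough. The third criterion has no counterpart. Read alone, the footnote therefore allows a delay for a subject whom Section 7.3 says must stop.

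The omitted criterion is an important one. Under Section 7.3, Grade 3 laboratory abnormalities do not by themselves force discontinuation, apart from the thrombocytopenia and liver criteria. Below 8 x and 5 x ULN, the concurrent rule is the only one of those liver criteria that compels stopping. It also shares its thresholds with the protocol's definition of potential DILI.

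This is a multi-site trial, and Section 7.4 directs sites to Appendix C for exactly these events. One site could record a delay on the footnote while another discontinues under Section 7.3 for the same laboratory result. The stake is consistent application of a liver-safety stopping rule, not an efficacy estimate.

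**Working it through.** The plan gives no figure to reproduce here. The check is whether the two rules can both apply to the same laboratory values.

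**Inputs.** Let A be AST or ALT and B total bilirubin, both in multiples of ULN.

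- Section 7.3, discontinue: A > 8, or B > 5, or (A > 3 and B > 2).
- Appendix C footnote, delay allowed: A ≤ 8 and B ≤ 5.

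**Overlap, one criterion at a time.**

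| Section 7.3 criterion | Also within A ≤ 8 and B ≤ 5? | Overlap |
|---|---|---|
| A > 8 | No, excluded by A ≤ 8 | None |
| B > 5 | No, excluded by B ≤ 5 | None |
| A > 3 and B > 2 | Yes | 3 < A ≤ 8 and 2 < B ≤ 5 |

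**Grid confirmation.** Both rules were evaluated in steps of 0.1 x ULN.

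- The conflicting values of A run from 3.1 to 8.0, which is 50 steps.
- The conflicting values of B run from 2.1 to 5.0, which is 30 steps.
- The overlap is 50 × 30 = 1,500 points. It matches the rectangle above exactly, with none outside it.

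The grid shows where the rules conflict. It says nothing about how often such values occur.

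**Worked case.** ALT 6 x ULN with bilirubin 3 x ULN:

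- Section 7.3: 6 > 3 and 3 > 2, so discontinue.
- Footnote: 6 ≤ 8 and 3 ≤ 5, so a delay is allowed.

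**After the fix.** With the footnote changed to A ≤ 8 and B ≤ 5 and not (A > 3 and B > 2), the overlap with each of the three criteria is 0 points. Every grid point then falls under exactly one of the two rules.

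**Frequency.** The documents do not allow an estimate. Table 5 has no bilirubin row, lists individual drug-related adverse events only when they reach 20% of subjects, and covers combination treatment only (N = 44). Section 7.3 applies with or without ipilimumab, so the rule reaches all 83 planned subjects (Section 13.3). That is the rule's scope, not a count of expected cases.

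**The case against.** The strongest reply is that this is a gap in generic guidance, already governed by the operative sections.

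- **Status of the texts.** Appendix C is labelled as recommended management, and Section 7.4 presents it as general guidance for all immuno-oncology agents. Section 7.3 is the trial-specific rule. A site that departs from Appendix C to follow Section 7.3 incurs no deviation.
- **Permissive wording.** The footnote says a delay is possible, not required. A site that discontinues complies with both texts.
- **Section 7.2.** Delay and discontinuation differ in practice only when redosing is considered, and there Section 7.2 repeats the bar on combined elevations.
- **Reporting.** Potential DILI is an SAE. Under Section 12.3 it goes to the Overall PI and, within 24 hours, to the drug supplier.
- **The missing figure.** The box that the asterisk qualifies cannot be seen. If it belongs to one grade branch, the conflict is narrower than the full rectangle.

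Much of this stands, and it limits the point to a minor one. Sections 7.2 and 7.3 would reasonably prevail, and the footnote does not authorise redosing. It does not remove the inconsistency, for four reasons:

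- No sentence says that Sections 7.1 to 7.3 override Appendix C. The Appendix C header excuses departures from Appendix C, not from Section 7.3, so a site relying on the footnote could commit a violation as Appendix D, Section 3.8, defines it.
- The Section 7.2 bullet names combined Grade 2 values and does not expressly address higher grades. It is also reached only after a delay has been recorded.
- Section 12.6 governs reporting, not dosing, and leaves out cases with initial cholestasis or another apparent cause.
- A narrower branch in the unseen figure would shrink the overlap. It would remove it only if the figure itself excluded concurrent elevations, and that cannot be checked.

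**Conclusion.** The point holds as a wording error in the footnote. One of the three liver criteria in Section 7.3 is affected. Because Section 7.2 refers back to the concurrent rule, Section 7.3 is evidently the intended text and the footnote is the one to correct.

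The practical consequence is possible inconsistent handling of what is probably a rare liver-safety event, with SAE reporting likely to bring many cases to central attention. No endpoint, sample size, power or error rate is touched. It is worth correcting but is not a major finding.

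The conclusion assumes that the footnote means what it says on its own and that the abnormality is drug-related, which is the setting of both texts. Confidence is medium because the hepatic figure is unavailable.

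**What to change.** Add an exclusion to the Appendix C hepatic footnote, for example: *unless AST or ALT > 3 x ULN and total bilirubin > 2 x ULN occur concurrently, in which case discontinue per Section 7.3*. When making the change, check that the figure's boxes agree with it.

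Add one sentence to Section 7.4 stating that Sections 7.1 to 7.3 govern wherever Appendix C differs. This would also settle any other difference between the generic algorithms and the trial's dosing rules.

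The cost is one clause and one sentence at the next amendment, with no added visits, tests or subjects.

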1. INTRODUCTION

The Dana-Farber/Harvard Cancer Center Multi-Center Data and Safety Monitoring Plan (DF/HCC DSMP) outlines the procedures for conducting a DF/HCC Multi-Center research protocol. The DF/HCC DSMP should serve as a reference for any sites external to DF/HCC that will be participating in the research protocol.

1.1 Purpose

To establish standards that will ensure that a Dana-Farber/Harvard Cancer Center Multi-Center protocol will comply with Federal Regulations, Health Insurance Portability and Accountability Act (HIPAA) requirements and applicable DF/HCC Standard Operating Procedures.

1.2 Multi-Center Data and Safety Monitoring Plan Definitions

DF/HCC Multi-Center Protocol: A research protocol in which one or more outside institutions are collaborating with Dana-Farber/Harvard Cancer Center where a DF/HCC investigator is the sponsor. DF/HCC includes Dana-Farber/Partners Cancer Care (DF/PCC) Network Clinical Trial Affiliates.

Lead Institution: One of the Dana-Farber/Harvard Cancer Center consortium members (Dana-Farber Cancer Institute (DFCI), Massachusetts General Hospital (MGH), Beth Israel Deaconess Medical Center (BIDMC), Boston Children's Hospital (BCH), Brigham and Women's Hospital (BWH)) responsible for the coordination, development, submission, and approval of a protocol as well as its subsequent amendments per the DFCI IRB and applicable regulatory guidelines (CTEP, Food and Drug Administration (FDA), Office of Biotechnology Activities (OBA) etc.). The Lead Institution is typically the home of the DF/HCC Sponsor.

DF/HCC Sponsor: The person sponsoring the submitted Multi-Center protocol. Within DF/HCC, this person is the Overall Principal Investigator who takes responsibility for initiation, management and conduct of the protocol at all research locations. In applicable protocols, the DF/HCC Sponsor will serve as the single liaison with any regulatory agencies (i.e. FDA, OHRP, etc.). The DF/HCC Sponsor has ultimate authority over the protocol and is responsible for the conduct of the study at DF/HCC and all Participating Institutions. In most cases the DF/HCC Sponsor is the same person as the DF/HCC Overall Principal Investigator; however, both roles can be filled by two different people.

Participating Institution: An institution that is outside the DF/HCC and DF/PCC consortium that is collaborating with DF/HCC on a protocol where the sponsor is a DF/HCC Investigator. The Participating Institution acknowledges the DF/HCC Sponsor as having the ultimate authority and responsibility for the overall conduct of the study.

Coordinating Center: The entity (i.e. Lead Institution, Medical Monitor, Contract Research Organization (CRO), etc) that provides administrative support to the DF/HCC Sponsor in order that he/she may fulfill the responsibilities outlined in the protocol document and DSMP, and as specified in applicable regulatory guidelines (i.e. CTEP Multi-Center Guidelines). In general, the Lead Institution is the Coordinating Center for the DF/HCC Multi-Center Protocol.

DF/HCC Office of Data Quality (ODQ): A group within DF/HCC responsible ensuring high-quality standards are used for data collection and the ongoing management of clinical trials, auditing, and data and safety monitoring. ODQ also coordinates quality assurance efforts related to multi-center clinical research.

DF/HCC Clinical Trials Research Informatics Office (CTRIO): A group within DF/HCC responsible for providing a comprehensive data management platform for managing clinical trial data.

2. GENERAL ROLES AND RESPONSIBILITIES

For DF/HCC Multi-Center Protocols, the DF/HCC Sponsor, the Coordinating Center, and the Participating Institutions are expected to adhere to the following general responsibilities:

2.1 DF/HCC Sponsor

The DF/HCC Sponsor, [REDACTED] will accept responsibility for all aspects of conducting a DF/HCC Multi-Center protocol which includes but is not limited to:

- Oversee the coordination, development, submission, and approval of the protocol as well as subsequent amendments.
- Ensure that the investigators, study team members, and Participating Institutions are qualified and appropriately resourced to conduct the protocol.
- Include the Multi-Center Data and Safety Monitoring Plan as an appendix to the protocol.
- Ensure all Participating Institutions are using the correct version of the protocol.
- Ensure that each participating investigator and study team member receives adequate protocol training and/or a Site Initiation Visit prior to enrolling participants and throughout trial's conduct as needed.
- Ensure the protocol will be provided to each participating site in a language understandable to all applicable site personnel when English is not the primary language.
- Monitor progress and overall conduct of the study at all Participating Institutions.
- Require all DFCI and Participating Institution Institutional Review Boards' (IRB), DF/HCC and other applicable (i.e. FDA) reporting requirements are met.
- Review data and maintain timely submission of data for study analysis.
- Act as the single liaison with FDA.
- Ensure compliance with all requirements as set forth in the Code of Federal Regulations, applicable DF/HCC requirements, HIPAA requirements, and the approved protocol.
- Commit to the provision that the protocol will not be rewritten or modified by anyone other than the DF/HCC Sponsor and as approved by BMS.
- Identify and qualify Participating Institutions and obtain accrual projections prior to extending the protocol to that site.

- Monitor accrual and address Participating Institutions that are not meeting their accrual requirements.

